5.3.2.1 Safety

Two large randomised, double blind, placebo-controlled Phase IIb-III studies have been conducted in patients with MS; 65 patients in study MS-ON for up to 6 months and 103 patients in study MS-SPI received 100 mg MD1003 TID for up to 12 months. Both studies have open label extension phases which are ongoing. The most commonly reported adverse events (>5% of patients) after treatment with MD1003 in these 2 completed randomised, double-blind, placebo-controlled studies, regardless of assessment of relationship to study treatment were nasopharyngitis, urinary tract infection, worsening of signs and symptoms of MS and MS relapse. The majority of reported adverse events were mild to moderate. Reported SAEs are consistent with the conduct of a trial in an MS patient population.

In completed studies with MD1003, a total of 4 serious adverse events (SAEs), reported in 4 patients and considered by investigators as being related to the study drug were reported. These SAEs included mucocutaneous rash, hypoglycaemia, transient myopathy and laboratory test interference.

In ongoing studies, one SAE (rash maculo-papular) in one patient with amyotrophic lateral sclerosis was considered as related to MD1003 by the investigator.

No deaths, SAEs, or AEs leading to treatment discontinuation with MD1003 were reported in the 4 healthy volunteer studies with MD1003 administered at doses up to 600 mg.

Based on MD1003 clinical and non-clinical data available, as well as the corpus of scientific and medical literature related to biotin, the following safety issues have been identified in patients treated with MD1003: interference with laboratory tests based on a biotin/streptavidin interaction, for which minimisation measures are in place (trial participation card and referral letter to general practitioner/hospital stating the subject has received a high biotin dose if a subject if withdrawn early), and a potential risk of teratogenicity observed in animal studies (rabbits). Since this study involves a single dose of biotin and subjects are planned to be discharged only after the administered dose has been eliminated, risk due to interference with laboratory results is considered

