to be very low and will be considered only if subjects are withdrawn early. In the case of early withdrawal, the risk minimisation measures above will be applied. In addition, some local allergic skin reactions have been observed. A single case of hypoglycaemia in an insulin-dependent patient and a single case of transient myopathy have also been reported in clinical trials. Adverse drug reactions reported in clinical trials to date are provided in [Table 2](#).

Table 2 Tabulated List of Adverse Reactions

| MedDRA System Organ Class | Adverse Reaction (Preferred Term) | Frequency Category |
|---|-----------------------------------|-----------------------|
| Metabolism and nutrition disorders | Hypoglycaemia ^a | Uncommon ^d |
| Skin and subcutaneous tissue disorders | Mucocutaneous rash ^b | Uncommon ^d |
| | Blister ^b | Uncommon ^d |
| | Eczema ^b | Uncommon ^d |
| Musculoskeletal and connective tissue disorders | Myopathy ^c | Uncommon ^d |

MedDRA: Medical Dictionary for Regulatory Activities

^a One patient (0.4%) with insulin-dependent diabetes experienced hypoglycaemic episodes, which occurred in the open-label phase of the studies approximately 1 year after initiation of MD1003. Episodes ceased when MD1003 was stopped and recurred on re-challenge.

^b During treatment with MD1003 in the double-blind placebo-controlled phases of the clinical studies, 1 (0.6%) patient developed a mucocutaneous rash, 1 (0.6%) patient cutaneous blisters and 1 (0.6%) patient eczema. No patients in the placebo group reported these events.

^c One (0.4%) patient developed transient myopathy, which occurred in the open-label phase of the studies 5 months after initiation of MD1003. The patient fully recovered when MD1003 was stopped.

^d Uncommon frequency category defined as $\geq 1/1000$ to $< 1/100$.

No serious adverse reactions have been listed as expected so far [\[1\]](#).

The safety profile of MD1003 is favourable, supporting the continuation of the clinical investigations program for the treatment of MS as planned.

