5.3.4 Pharmacokinetics and Product Metabolism in Animals

Full details of PK and absorption, metabolism, distribution and elimination (ADME) data can be found in the Investigator's Brochure [1].

In the GLP Study MD1003-ADME-RAT, the radioactivity was rapidly eliminated from plasma after intravenous administration of 10 mg/kg ¹⁴C-MD1003. After oral administration of 30 mg/kg ¹⁴C-MD1003 (human equivalent therapeutic dose), the radioactivity was rapidly absorbed and after a first phase of rapid elimination from the plasma, the radioactivity was then slowly eliminated.

At physiological doses of [¹⁴C] biotin (88 nmol/kg body weight) given orally to pigs, the plasma concentration profile best fitted a tri-exponential equation [9], which corresponds to a tricompartamental open model. Disappearance curves of total ¹⁴C and of [¹⁴C] biotin were similar. Biotin pharmacokinetics after intravenous injection of [¹⁴C] biotin was marked by a very short half-life of the initial distribution phase (7 min), followed by a slower plasma elimination phase (T_{1/2}, β of 1.43 h) and a long apparent terminal half-life T_{1/2}, γ estimated at 22 h. The rapid initial distribution phase was shown to correspond to the disappearance of biotin from the plasma (central compartment) to the peripheral compartments, such as the total body water pool or tissue pools [9].

The retention over many days of a substantial portion of the administered dose may occur as a consequence of the metabolic trapping of biotin into cells: conversion of biotin to intermediates such as biotinyl-adenosine monophosphate and biotinyl-CoA, or binding of biotin to proteins such as carboxylases and histones [9]. The half-life of pyruvate carboxylase was determined to be 28 h and 4.6 days for acetyl-CoA carboxylase [10].

Overall, PK data obtained with MD1003 confirmed the literature data and completed the PK properties of biotin:

- Biotin is rapidly absorbed by the oral route in animals

- At the equivalent therapeutic dose in rats (30 mg/kg), biotin is not completely absorbed
- At very high doses (up to 3000 mg/kg), plasma exposure does not significantly increase, suggesting that the transport is saturated
- The major route of elimination is urinary and most of the biotin is excreted unchanged
- There was no evidence of accumulation after once daily repeated dosing in animals

6 Rationale

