8.1 Study Plan

[figure not shown]
This is a single-centre, open-label, non-randomised, single oral dose study in healthy male subjects. It is planned to enrol 6 subjects to ensure 4 evaluable subjects.

Each subject will receive a single oral administration of a capsule containing 100 mg MD1003 and NMT 2.22 MBq (approximately 60.0 µCi) [¹⁴C], in the fasted state.

The study design is presented in [Figure 1](#). Subjects will be screened to participate in the study up to 28 days before dosing. Subjects will be admitted to the clinical unit on the evening of Day -1 prior to IMP administration.

Subjects will be dosed on the morning of Day 1 following an overnight fast and will remain resident in the clinical unit until up to 168 h after dosing (up to Day 8). It is planned that subjects will be released as a group when all subjects have achieved a mass balance cumulative recovery of >90% or if <1% of the dose administered has been collected in urine and faeces within 2 separate consecutive 24 h periods. This may result in the subjects being discharged as a group prior to completion of the planned residency period. Once the discharge criteria or the planned residency period has been achieved, collection of all samples (blood, urine and faeces) will be stopped and the subjects will undergo discharge assessments. If the mass balance criteria have not been met by all subjects by Day 8, the residency period for the subjects not achieving the release criteria may be extended up to a maximum of an additional 48 h (up to Day 10) for further collection of urine and/or faeces. If the release criteria have still not been met by Day 10, or if any additional residency is not considered appropriate or necessary, then home collections of urine and/or faeces may be requested at the discretion of the investigator for individual subjects.

Figure 1 Study Sequence

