8.3 Subject Withdrawal

If a subject wishes to leave the study at any time, they will be permitted to do so. Every reasonable effort will be made by Quotient Sciences to complete a final assessment/discharge procedures. Quotient Sciences will advise the sponsor of the withdrawal of any subject from the study.

Early withdrawal is defined as the date of the decision to withdraw the subject from the study. Subject completion is defined as the date of the last procedure conducted or last contact (ie phone call) for that subject.

If a subject requests to leave the clinical unit earlier than the planned discharge time eg due to unforeseen personal circumstances, but aims to return to the clinical unit to complete the study, this will be documented as a subject self-discharge and a protocol deviation. The subject must complete the planned assessments/discharge procedures before discharge from the clinical unit and will return for the next study period/assessments, as planned.

Subjects will be withdrawn from the study drug(s) for the following reasons:

- Experiencing a serious or severe AE including but not limited to:
 - corrected QT interval by Fridericia's formula (QTcF) of >500 msec or increase in QTcF interval of >60 msec from baseline (confirmed following a repeat ECG)
 - alanine aminotransferase (ALT) concentration >3 × the upper limit of the reference range (confirmed following a repeat ALT blood test)
- Experiencing a 25% decrease in creatinine clearance (CLcr)
- Termination of the study
- Upon the subject's request (withdrawal of consent)
- Significant deviation from the protocol
- Concurrent illness that would compromise subject safety of study data interpretation or requirement for prohibited medication
- At the discretion of the investigator

For the purpose of withdrawal criteria, baseline will be considered as pre-dose Day 1 measurement.

For a subject who withdraws because of an IMP-related AE, every effort will be made to ensure the subject completes follow-up procedures.

Early termination of the study will be distinguished from withdrawal of consent by the subject to participate in any further activities.

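### The biotin assay-interference measures are triggered only by early withdrawal, yet sections 8.1, 8.3 and 10.3.3 let subjects leave by other routes before elimination has been shown

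*Protocol*

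**What the plan says.** Section 5.3.2.1 names two safety issues for MD1003: interference with tests that use biotin/streptavidin binding, and possible teratogenicity. Laboratory test interference is also one of the four related serious adverse events it reports from completed studies. The measures against interference are described as a "trial participation card and referral letter to general practitioner/hospital stating the subject has received a high biotin dose if a subject if withdrawn early".

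For this study the section gives two reasons for thinking the risk small: there is only one dose, and "subjects are planned to be discharged only after the administered dose has been eliminated". The risk is therefore judged "to be very low and will be considered only if subjects are withdrawn early", and the section adds: "In the case of early withdrawal, the risk minimisation measures above will be applied".

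The rules for leaving the unit are elsewhere. Section 8.1, repeated in substance in 10.3.3, plans a group release on recovery criteria. Discharge assessments follow either those criteria or the end of the planned residency at Day 8. An extension to Day 10 is optional. "If the release criteria have still not been met by Day 10, or if any additional residency is not considered appropriate or necessary", home collections may be requested. Section 8.3 covers the subject who leaves ahead of time but means to come back: "this will be documented as a subject self-discharge and a protocol deviation". Section 10.3.4 gives every subject a card and describes it only as carrying contact numbers.

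**The concern.** The sponsor has decided that an outside clinician needs to be told about the biotin dose when a subject leaves before elimination is assured. The trigger chosen for that is early withdrawal. It works only if withdrawal is the sole way of leaving before elimination, and the protocol itself describes two others. A subject on either route could have a biotin-sensitive test misread by someone who was never informed, and the site would have followed the protocol exactly. Preventing this is the purpose of the card and letter. No endpoint or analysis is affected; the point concerns whether a stated safety mitigation reaches the people its own reasoning covers.

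**Working it through.** This is mainly a comparison of texts. The arithmetic only indicates scale.

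**Step 1. Each way of leaving, set against the premise and the trigger.**

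| Route | Section | Elimination shown? | Early withdrawal? | Measures triggered? |
|---|---|---|---|---|
| Group release, criteria met | 8.1, 10.3.3 | By the protocol's own criteria | No | No; consistent with the premise |
| Withdrawal from the study | 8.3 | Not necessarily | Yes | Yes |
| Leaving at Day 8 or Day 10, criteria unmet | 8.1, 10.3.3 | No | No | No |
| Self-discharge with intent to return | 8.3 | No; may occur at any time after dosing | No; recorded as a deviation | No |

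The last two rows are the gap. Section 8.3 ties early withdrawal to a decision to withdraw the subject from the study, so neither row falls under it. The discharge conditions in section 10.3.3 mention neither the card nor the letter.

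**Step 2. What an unmet recovery criterion means.** The dose is 100 mg (section 8.1: "Each subject will receive a single oral administration of a capsule containing 100 mg MD1003"). A subject who fails the criterion of more than 90% recovery has at least 100 mg × (1 − 0.90) = 10 mg-equivalents of total radioactivity unaccounted for. This is not an amount of circulating biotin. It includes metabolites, biotin bound in cells, unabsorbed dose and collection losses. Section 5.3.1 puts oral bioavailability at about 50%.

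**Step 3. How much could be circulating at Day 8 or Day 10.** The only terminal plasma half-life in the protocol is 22 h, in pigs after intravenous dosing (section 5.3.4). Assuming it applies, the fraction of the terminal-phase amount left at time t is 0.5^(t/22):

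- Day 8, t = 168 h: 0.5^(168/22) = 0.005, about 0.5%.
- Day 10, t = 168 + 48 = 216 h: 0.5^(216/22) = 0.001, about 0.1%.

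Section 5.3.4 also gives enzyme half-lives of 28 h and 4.6 days (110.4 h). The same formula then gives 1.6% and 0.5% at the two times for 28 h, and 35% and 26% for 4.6 days. Those values describe turnover of carboxylases to which biotin is bound. They do not describe free biotin in plasma, so they are no basis for sizing assay interference.

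**Step 4. Self-discharge.** Section 8.3 sets no earliest time, so a subject could leave within hours of dosing. The protocol gives no human plasma profile for this dose and no interference threshold, so no figure is attached to this route.

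**The case against.** The strongest reply is that section 5.3.2.1 speaks only of what is planned. Section 8.1 also plans release on recovery criteria, so the two plans agree and the other routes are contingencies. That is fair for the premise but does not rescue the trigger. The safeguards exist for contingencies, and leaving with criteria unmet is itself written into section 8.1.

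A reader might infer that subjects go home with a meaningful dose still on board, pointing to the 10 mg-equivalents above, or to section 5.3.4, where "The retention over many days of a substantial portion of the administered dose may occur". The documents do not support this. Unrecovered radioactivity is not circulating biotin, and that sentence attributes retention to trapping inside cells. Section 5.3.1 reports very low concentrations after 24 h and no storage in rats. Nor does the criterion of under 1% of dose on two consecutive days show the contrary: although it carries no minimum total recovery, excretion that low suggests little mobile drug remains at plasma half-lives like the one quoted.

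A reader might also infer that these subjects leave with no card at all. That is not established. Everyone receives the section 10.3.4 card, and the text does not say whether it is the participation card or mentions biotin. In section 5.3.2.1 the condition about withdrawal could grammatically attach to the letter alone, although the later sentence applying the measures on early withdrawal favours attaching it to both.

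Other controls exist. Section 8.3 requires a self-discharging subject to complete discharge procedures and return. Section 10.3.3 requires investigator authorisation when its conditions are unmet. Section 8.3 lists significant protocol deviation as a reason for withdrawal, so a self-discharge might be reclassified. None of these requires that the outside clinician be told. The points reduce the likely risk; they do not close the gap.

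**Conclusion.** The concern holds as a mismatch between premise, trigger and discharge routes. Subjects who leave at Day 8 or Day 10 with criteria unmet, and subjects who self-discharge, fall outside the trigger although elimination has not been shown. It matters most for self-discharge soon after dosing. For Day 8 to 10 the practical risk is probably small, on the assumption that a pig intravenous half-life is a rough guide to free biotin in man. With six planned healthy subjects, one dose each and no stated interference threshold, the clinical risk cannot be quantified, and no figure here should be read as doing so. The gap is still worth closing, because it concerns an identified safety issue and the correction is nearly free.

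**What to change.** Reconcile section 5.3.2.1 with sections 8.1, 8.3 and 10.3.3 so that three things agree: the statement about elimination before discharge, the event that brings the existing card and letter into use, and the routes by which a subject may leave. State whether the section 10.3.4 card is the trial participation card and whether it mentions the biotin dose. How the passages are brought into line is a clinical decision for the sponsor and investigator; this review does not propose a rule.

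The cost is a few sentences in a protocol amendment. Dose, residency, release criteria, samples and analyses stay as they are. The risk statement in section 5.3.2.1 may read slightly less favourably.

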5.3.3 Efficacy

An open label pilot study was conducted in MS patients (n=23) using high doses of biotin and demonstrated that biotin could favourably effect disease progression in patients with progressive MS [\[5\]](#).

MS-SPI Trial: The Multiple Sclerosis-Spinal (MS-SPI) study (randomised double-blind study) was conducted to demonstrate the superiority of MD1003 300 mg/day over placebo in patients with progressive MS (n=154). The primary outcome measure was the proportion of patients who demonstrated improvement in a composite measure of Expanded Disability Scale Status (EDSS) and timed 25-foot walk. The primary endpoint was reached with 13 (12.6%) patients treated with MD1003 who achieved clinical improvement in MS-related disability at month 9, confirmed at month 12, compared with none of the placebo-treated patients (p=0.0051). Results of clinician and patient global impression of change measure (CGI/SGI) also showed statistically significant differences in favour of the MD1003 group. The mean change EDSS was stable in MD1003 treated patients while it progressively worsened in placebo active arms and compared to previous published studies (p=0.69) [\[7\]](#). An open label extension study continues.

MS-ON Trial: The effect of MD1003 in MS patients with permanent visual loss following optic neuritis (ON) was assessed in another controlled clinical study, MS-ON, enrolling 93 patients. Following a 6-month treatment, there was no clinically significant difference between the MD1003 group and the placebo group, with no increase in the mean change of visual acuity in all groups. A positive trend was observed in the progressive optic neuropathy subgroup (n=31), which is consistent with findings of Study MS-SPI, where MD1003 showed efficacy in patients with a progressive form of MS [8].

These results support that targeting neuron/oligodendrocyte metabolism represents a novel disease modifying therapy approach in progressive MS.

Overall, results of the double-blind and extension phases of MS-SPI and MS-ON studies showed a benign safety profile and suggest a durable treatment effect of MD1003 in patients with progressive MS.

A larger international randomised placebo-controlled trial (SPI2) is ongoing in patients with progressive MS.

5.3.4 Pharmacokinetics and Product Metabolism in Animals

Full details of PK and absorption, metabolism, distribution and elimination (ADME) data can be found in the Investigator's Brochure [1].

In the GLP Study MD1003-ADME-RAT, the radioactivity was rapidly eliminated from plasma after intravenous administration of 10 mg/kg ¹⁴C-MD1003. After oral administration of 30 mg/kg ¹⁴C-MD1003 (human equivalent therapeutic dose), the radioactivity was rapidly absorbed and after a first phase of rapid elimination from the plasma, the radioactivity was then slowly eliminated.

At physiological doses of [¹⁴C] biotin (88 nmol/kg body weight) given orally to pigs, the plasma concentration profile best fitted a tri-exponential equation [9], which corresponds to a tricompartamental open model. Disappearance curves of total ¹⁴C and of [¹⁴C] biotin were similar. Biotin pharmacokinetics after intravenous injection of [¹⁴C] biotin was marked by a very short half-life of the initial distribution phase (7 min), followed by a slower plasma elimination phase (T_{1/2}, β of 1.43 h) and a long apparent terminal half-life T_{1/2}, γ estimated at 22 h. The rapid initial distribution phase was shown to correspond to the disappearance of biotin from the plasma (central compartment) to the peripheral compartments, such as the total body water pool or tissue pools [9].

The retention over many days of a substantial portion of the administered dose may occur as a consequence of the metabolic trapping of biotin into cells: conversion of biotin to intermediates such as biotinyl-adenosine monophosphate and biotinyl-CoA, or binding of biotin to proteins such as carboxylases and histones [9]. The half-life of pyruvate carboxylase was determined to be 28 h and 4.6 days for acetyl-CoA carboxylase [10].

Overall, PK data obtained with MD1003 confirmed the literature data and completed the PK properties of biotin:

- Biotin is rapidly absorbed by the oral route in animals

- At the equivalent therapeutic dose in rats (30 mg/kg), biotin is not completely absorbed
- At very high doses (up to 3000 mg/kg), plasma exposure does not significantly increase, suggesting that the transport is saturated
- The major route of elimination is urinary and most of the biotin is excreted unchanged
- There was no evidence of accumulation after once daily repeated dosing in animals

6 Rationale

6.1 Study Rationale

This study is being conducted to investigate the oral PK, mass balance and metabolite profiling and identification of [¹⁴C]-MD1003.

6.2 Dose Rationale

The therapeutic daily dose of biotin is 300 mg given as 100 mg TID; therefore, a 100 mg single dose is considered the appropriate dose to investigate in an ADME study. This dose is not expected to result in any significant adverse effects in a healthy volunteer population.

The dose of radioactivity has been determined following review of human dosimetry calculations provided by Public Health England (PHE). The associated radiation exposure will fall within International Commission on Radiological Protection (1992) Guidelines for Category IIa studies (0.1 to 1 mSv). The dose of radioactivity will be no more than 2.22 MBq (60.0 µCi).

To ensure that the [¹⁴C] drug product(s) does not exceed the limit for radioactive dose approved by the Administration of Radioactive Substances Advisory Committee (ARSAC), the target specific activity of the drug substance will be set at 95% of 90% of the threshold radioactive dosing limit. This takes into account the allowed tolerances during the manufacture of the drug product (± 5% range and drug substance ± 10% range). This provides continued assurance for compliance with the ARSAC-approved limit for drug product radioactivity dose.

